Musculoskeletal pain among E-sport athletes

Protocol version 1.0, date 26-03-2019

Background

Musculoskeletal (MSK) pain and injuries are common in endurance sports where athletes are required to perform at high intensity for an extended period of time (1). In the short term, MSK pain may significantly impair the athletes' performance, which can lead to unwanted time-off from practice and competitive tournaments (1). Ultimately, MSK pain may lead to complete withdrawal from sports and physical activity and long-term health issues (1–3). Previous studies found an association between training load, MSK pain and performance. These results indicate that an athlete may experience MSK pain or get injured from both too low and to high training loads (1,4).

Electronic sport (E-sport) also known as competitive gaming is defined by Hamari and Sjöblom as *“a form of sports where the primary aspects of the sport are facilitated by electronic systems; the input of players and teams as well as the output of the E-sport system are mediated by human-computer interference”* (5). The expected yearly growth-rate of E-sport is estimated to be 25% and approximately 190 million people around the world are actively involved in E-sport (6,7). E-sport also encompass structured tournaments which offer millions in prizemoney for the winning team (6,8). Furthermore, the tournaments are often streamed lived through the internet, so that the hundreds of millions of spectators from all over the world can follow their favourite teams in action (5,6). At present it is debated whether or not E-sport should be regarded as an actual sport instead of a recreational activity (8). The lack of physical activity and bodily movement is today the strongest argument against recognizing E-sport as sports (8). Nevertheless, the international demand for recognition is growing, and acceptance of E-sport as an actual sport may be inevitable (8). There is only few data on MSK pain in E-sport, however a small study with 65 participants found that 41% suffered from back or neck pain and more than 1 in 3 had pain related to the wrist (9). E-sport athletes have to perform for an extended period of time, similar to athletes from traditional endurance sport. As such, MSK pain in E-sport may be associated with training load like it is seen in other sports (4). Overall, MSK pain in E-sport could be an unrecognised issue. To provide healthcare professionals with an optimal starting point for managing these issues, there is a need for well-conducted studies on the prevalence of MSK pain among E-sport athletes. In addition, it is highly relevant to investigate if training loads related to E-sport and physical activity levels are different among athletes with MSK pain compared to athletes without MSK pain.

Aims

The aims of this questionnaire-based cross-sectional study are to; I) investigate the prevalence of MSK pain in E-sport athletes, II) assess if training loads among athletes with MSK pain are different from athletes without MSK pain, III) investigate if physical activity levels among athletes with MSK pain are different from athletes without MSK pain and IV) descriptively present data on participant characteristics, sleep patterns, physical activity levels and utilization of healthcare professionals and pain medication. It is hypothesised that E-sport athletes with MSK pain have a higher training load compared to athletes without MSK pain. Moreover, it is hypothesised that E-sport athletes with MSK pain have a lower level of physical activity compared to athletes without MSK pain.

Method

This project will be conducted at the Department of Physiotherapy at UCN, Aalborg, Denmark and the protocol will be developed from The Strengthening the Reporting of Observational Studies in Epidemiology (STROBE) Statement (10). The project will in addition be pre-registered on www.Clinicaltrials.gov, prior to enrolment of the first participant. Participants will be provided with oral and written information regarding the study, before providing written informed consent.

Recruitment

We aim to recruit 200 E-sport athletes between 15 and 35 years of age. We estimate that 200 athletes will be an appropriate sample to investigate the prevalence of MSK pain within the E-sport community. The rationale for the age-range is based on numbers from DGI which is a national organization in Denmark which aim to strengthen the community-based sport clubs and associations (11). Approximately 60% of the E-sports athletes registered with DGI are between the ages of 15 and 35 (12). Athletes will be recruited from community-based and/or professional E-sport clubs and teams. Moreover, educational institutions who offer their students the opportunity to participate in E-sport will be contacted as well and invited to participate. Educational institutions and E-sport clubs and teams in Denmark will be identified through web-based searches and through the authors' network. Initial contact will be established through e-mail or via telephone. Members from the research group will subsequently visit clubs, teams and educational institutions who initially shows an interest for the project. At this occasion the members of the research group will give a short presentation of the project, answer questions regarding the project and distribute the questionnaire to those athletes who wants to participate.

Distribution of questionnaires

Prior to initiation of the study, the questionnaire will be pilot tested and evaluated regarding time to complete, relevance and comprehensibility. After the following optimization, the questionnaire will be distributed for all participating athletes as an online survey.

Eligibility criteria

E-sport athletes from Denmark between the age of 15 and 35, who are participating actively in E-Sport through a club and/or team based in the community, at an educational institution or in a private organization are eligible for enrolment. In addition, eligible athletes are required to participate in E-sport through a computer-based game. As such, athletes who primarily compete through other medias or consoles are not eligible for participation.

Participant information and outcome

Information regarding MSK pain, utilization of healthcare professionals and pain medicine, physical activity levels, E-sport related training load and sleep patterns will be obtained through this questionnaire-based study.

Participant characteristics

Enrolled athletes will be asked to provide; name, e-mail, phone number, age, gender, height, weight, educational level, smoking status, where they participate in E-Sport (e.g. community-based or educational institution), which league they are affiliated with (e.g. DGI-league or ESD-league) and which is their primary game (e.g. Counter Strike: Global Offensive, Fortnite or PlayerUnknown's Battleground).

Musculoskeletal pain

The primary outcome for the study will be if the athletes have had any MSK pain during the previous week. The answer to the primary outcome will be dichotomized (yes/no). Participants will also be asked about the location and number of pain sites. If the athlete has pain at more than one site, they will be asked to state at which site they experience their primary pain complaint. In relation to the site of the primary pain complaint, the athletes are asked to state the worst pain intensity they have experienced during the previous week. Pain intensity will be assessed with an 11-point numeric pain rating scale (0=no pain; 10=worst possible pain). The athletes will in addition be asked about pain frequency (daily, weekly, several times per week, monthly, rarely). To investigate the level of pain interference, athletes will be asked if their MSK pain affect their ability to engage in E-sport.

Eye fatigue

Within a group of E-sport athletes, one study found that 52% reported eye fatigue (9). As such, we are also interested in investigating if the included athletes experience eye fatigue in relation to E-sport participation.

Training load related to E-sport

Athletes will be asked how many hours per week they spend on structured E-sport with is defined as training with a coach being present. In addition, they are asked how many hours per week they train without a coach present (e.g. when they are at home). Time spend on training without a coach present will be defined as unstructured training. The total E-sport related training load will be assessed by combining the number of hours the athletes engage in structured and unstructured E-Sport.

Healthcare utilization

In order to investigate care-seeking behaviour regarding MSK pain within the study population, the athletes will be asked if they have had any treatment from a healthcare professional during the previous 3 months for MSK pain. In addition, participants will be asked if they currently use any pain medication, which type of medication they use and how frequent. The athletes are also asked to describe the reason for using pain medicine.

Level of physical activity

Physical activity levels will be assessed with the Danish version of the International Physical Activity Questionnaire (IPAQ) short form. This survey is comprised of 7 items which assess time spend on physical activity at vigorous and moderate intensity, walking and sitting during the previous 7 days.

Sleep patterns

To assess sleep patterns the athletes will be asked how many hours they sleep during the night. In order to investigate the quality of sleep the athletes will be asked if they experience trouble falling asleep, if their sleep is interrupted during the night and if they feel tired in the morning. This approach has been used previously to investigate sleep patterns (3).

Data analysis

The prevalence of MSK pain within the study population will be presented in absolute numbers and as percentage values. To investigate if E-sport related training loads differ among athletes with and without MSK pain we will use total E-sport related training load (N hours spend on structured E-sport + N hours spend on unstructured E-sport). An independent sample t-test will be applied for this comparison if data are normally distributed. To assess if physical activity levels are different among athletes with and without

MSK pain we will use the responses from the IPAQ short form. For this comparison we will use an independent sample t-test or the Wilcoxon rank-sum test. Participant characteristics, distribution and number of MSK pain sites, utilization of health professionals and pain medicine, physical activity levels, training loads and sleep patterns will be presented descriptively. The data will be presented with means, standard deviations and 95% confidence intervals. Non-parametric data will be presented with absolute numbers and as percentage values, medians and range.

Ethics

Prior to undertaking the study, approval was sought from the local ethics committee in the Northern part of Jutland in Denmark, however according to Danish law (*Bekendtgørelse af lov om videnskabetisk behandling af sundhedsvidenskabelige forskningsprojekter §14 stk. 2*) no ethical approval is need.

Data proception

This study will adhere to the Helsinki declaration and person data will be collected and stored in accordance with the General Data Protection Regulation (GDPR).

Perspective

Arguably, staying pain – and injury free while participating in sports is the most optimal way to become a top-level athlete (8). The same logic could be applicable for E-sport athletes. As such, it is possible that highly engaged E-sport athletes will sustain injuries or experience MSK pain because of their choice of recreational activity. However, data on MSK pain among E-sport athletes is lacking. The national federation of E-sport in Denmark, *eSport Denmark*, was established in 2007 and is working towards branding, developing and expanding E-sport to the Danish population (13). Moreover, E-sport Denmark is collaboration with DGI to help establish community-based E-sport clubs and teams all over Denmark (14). As such, we are witnessing a paradigm shift where players organise themselves in teams and engaging in training sessions with coaches at a physical location. As the awareness and interest for participating in E-sport is on the rise, there is a need to collect data on the health status among E-sport athletes, in order to provide healthcare professional with the right tool and knowledge to help E-sport athletes to stay active within their sport.

References

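### Do weekly E-sport hours without a recall period, and a pain-interference item named in no analysis, undermine the training-load comparison?

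*Combined protocol and SAP*

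**What the plan says.** Training load related to E-sport introduces the first of two hours items: "Athletes will be asked how many hours per week they spend on structured E-sport". The second asks for weekly hours without a coach, and the sum of the two is the total load. Neither item is given a recall period.

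Other items are anchored in time. In Musculoskeletal pain, "The primary outcome for the study will be if the athletes have had any MSK pain during the previous week". The IPAQ covers seven days, and treatment by a healthcare professional covers three months.

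Aim II is to "assess if training loads among athletes with MSK pain are different from athletes without MSK pain". The accompanying hypothesis has a direction: "It is hypothesised that E-sport athletes with MSK pain have a higher training load compared to athletes without MSK pain". Data analysis compares total hours between athletes with and without pain.

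Musculoskeletal pain also collects whether pain affects taking part in E-sport. Data analysis uses this item in no comparison and leaves it out of the descriptive list.

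Two further statements bear on the point. Eligibility is limited to athletes "who are participating actively in E-Sport through a club and/or team". Before launch, "the questionnaire will be pilot tested and evaluated regarding time to complete, relevance and comprehensibility", and it is then to be optimised.

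**The concern.** The Background says that pain in endurance athletes may impair performance, "which can lead to unwanted time-off from practice and competitive tournaments", and it draws the parallel itself: "E-sport athletes have to perform for an extended period of time, similar to athletes from traditional endurance sport". If that carries over, some athletes with pain will already be playing less. Without a stated period, one athlete may report a usual week and another the past week, so the hours may be a mixture that includes recent cutbacks. That would lower the mean in the pain group and work against the hypothesis, so a null result in aim II would be hard to read.

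The one item that might hint at this, pain interference, has no stated use. A recall period cannot be supplied once the answers are in, so the time to raise the point would be before the pilot.

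**Working it through.** The plan has no figure of its own to reproduce here. It gives a target of 200 athletes and no expected hours, standard deviation (SD) or cutback.

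**1. Planned precision of aim II.** Assume 41% of 200 = 82 athletes with pain and 118 without. The 41% is the Background's figure for back or neck pain in 65 players, borrowed here for any pain. Assume an SD of 6–12 h. The 95% half-width is t(198) × SD × √(1/82 + 1/118) = 1.972 × SD × 0.1438, which is 1.70 h at SD 6 and 3.40 h at SD 12.

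**2. Size of a cutback effect.** Shift = share of the pain group reporting cut hours × size of cut × that group's usual mean. All three inputs are assumed, with means of 10–30 h:

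| Share | Cut | Shift |
|---|---|---|
| 10% | 10% | 0.1–0.3 h |
| 20% | 25% | 0.5–1.5 h |
| 30% | 50% | 1.5–4.5 h |

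The first two rows lie below even the smallest half-width in step 1. Only the third can exceed it.

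**3. How much of this comes from the missing period?** Split the share into s_old, athletes who cut back long enough ago that their usual week is already reduced, and s_new, athletes whose cut shows only in the past week. Let m be the proportion who read the question as the past week.

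- Usual-week wording: shift = s_old × cut × mean.
- No stated period: shift = (s_old + m × s_new) × cut × mean.
- Past-week wording: shift = (s_old + s_new) × cut × mean.

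The part due to the wording is m × s_new × cut × mean. It is zero if everyone answers for a usual week, and it can never exceed the full shift in step 2. The documents give neither m nor s_new. A past-week period, which would match the pain item, makes the shift largest, so fixing a period does not in itself help. The s_old term remains under every wording.

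**4. What a table by interference would show.** Suppose, favourably, that those who report interference are exactly those who cut back. With 82 in pain, shares of 10%, 20% and 30% give 8 v 74, 16 v 66 and 25 v 57. Half-width = t(80) × SD × √(1/n1 + 1/n2), with t(80) = 1.990; the range runs over SD 6–12 h.

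| Interfering v not | Half-width | Assumed cut among cutters |
|---|---|---|
| 8 v 74 | 4.4–8.9 h | 1–3 h |
| 16 v 66 | 3.3–6.7 h | 2.5–7.5 h |
| 25 v 57 | 2.9–5.7 h | 5–15 h |

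The mild case could not be seen, the middle case would mostly be unclear, and the extreme case would generally show. The item asks about ability, not hours lost. It is related to severity, and as described it has no recall period either.

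**5. Is the interference item singled out?** No. Data analysis also leaves pain intensity, pain frequency and eye fatigue off its descriptive list. Sleep hours, pain frequency and eye fatigue have no stated period either. The pattern is brevity in a short protocol, not a decision to set one item aside.

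**The case for a change.** The strongest reply is that a bias smaller than the confidence half-width can still cost a great deal. Assume a no-pain mean of 20 h, SD 10 h and a true difference of 4 h, so the pain group's usual mean is 24 h. If 25% of athletes with pain cut their hours by 25%, the observed difference is 4 − 0.25 × 0.25 × 24 = 2.5 h, and power falls from 79.5% to 41%. The difference vanishes when share × cut reaches 4/24 = 1/6. The omission cannot be repaired later, and rewording two questions before the pilot costs almost nothing.

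The arithmetic stands, but it shows what pain-driven cutback could do to any cross-sectional comparison of hours. It does not show what the missing recall period does. The mean, SD, true difference and cutbacks are all assumed, and the Background supplies only an analogy from endurance sport. Because active participation is required for entry, full withdrawal is not at issue, only reduced hours.

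The point about irreversibility would carry weight if the questionnaire were known to lack a period. It is not among the documents, the protocol summarises items without reproducing their wording, and the planned pilot is where an ambiguous question should come to light.

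**Conclusion.** No change to the plan is needed. The protocol's silence on the recall period is real, and so is the absence of the interference item from Data analysis. Both are gaps in written detail that the investigators can be expected to fill sensibly. Hours per week in the present tense reads as usual hours, and a pain item collected for a stated purpose would ordinarily be described alongside the others.

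Aim II asks about a difference, and the planned comparison answers that. Its limit is that temporal order is unknown, which belongs to the design and would remain under usual-week wording. Under the assumptions above, the total cutback effect is 0.1–4.5 h per week. The part due to the wording lies between zero and that total, and nothing in the documents narrows it. A table of hours by interference would be an optional description with a half-width of about 2.9–8.9 h on the contrast that matters, and it would alter neither the test nor its conclusion.

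Repeating the questionnaire's reference period in the protocol and completing the descriptive list would be tidy editing, with no planned result depending on it. The primary prevalence estimate is untouched.

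### The item meant to measure care-seeking asks only about treatment received, so it would tend to understate use of healthcare professionals by an unknown amount

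*Combined protocol and SAP*

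**What the plan says.** The Healthcare utilization section opens with the purpose of the item: "In order to investigate care-seeking behaviour regarding MSK pain within the study population". The same sentence then describes the item: "the athletes will be asked if they have had any treatment from a healthcare professional during the previous 3 months for MSK pain". The rest of that section is about medicines: "participants will be asked if they currently use any pain medication, which type of medication they use and how frequent", followed by the reason for use.

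The broader construct appears in three other places. Aim IV undertakes to describe "utilization of healthcare professionals and pain medication". The section on participant information and outcome lists the use of professionals among the information to be collected. The Data analysis section states that "utilization of health professionals and pain medicine, physical activity levels, training loads and sleep patterns will be presented descriptively".

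The document does not define treatment and does not reproduce the questionnaire. It does plan a pilot: "the questionnaire will be pilot tested and evaluated regarding time to complete, relevance and comprehensibility", with optimization before the survey goes out.

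**The concern.** Seeking care is something the athlete does. Receiving treatment depends also on what the professional decides. A visit that ends in an examination, a referral or a decision not to treat is care-seeking and is use of a professional, yet a literal reading of the item calls for a no. Advice is less clear, because some athletes will count it as treatment and others will not.

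For a descriptive aim the reported percentage is itself the result. If the item is narrower than its label, the published figure on use of professionals will tend to be too low, and a larger sample does not cure that. Contacts without treatment cannot be recovered afterwards from answers to a question about treatment.

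**Working it through.** **Step 1: construct against item.** The plan has no figure to reproduce here, so the main check is of the text.

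| Place in the protocol | What it covers |
|---|---|
| Healthcare utilization, purpose | Care-seeking for MSK pain |
| Aim IV; participant information and outcome; Data analysis | Use of healthcare professionals |
| Healthcare utilization, item | Treatment from a professional, previous 3 months, for MSK pain |

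The first two rows include contacts without treatment. The third does not, as described.

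**Step 2: does another item fill the gap?** The medication questions cover current use, type, frequency and reason. The Musculoskeletal pain section covers presence, sites, worst intensity, frequency and effect on E-sport participation. Neither asks about a consultation, an assessment or advice. No section states that treatment is to be read as including them.

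**Step 3: direction and size.** Let *p* be the true proportion who sought care. Let *s* be the share of those who answer no because they were not treated. If nobody who did not seek care answers yes:

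- recorded proportion = *p* × (1 − *s*)
- relative bias = −*s*
- absolute bias = −*p* × *s*
- athletes missed = *N* × *p* × *s*

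The documents supply only the planned *N*: "We aim to recruit 200 E-sport athletes between 15 and 35 years of age". Values for *p* and *s* are assumptions, so a range is shown. The last column is 1.96 × √(*r*(1 − *r*)/200), where *r* is the recorded proportion.

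| Assumed *p* | Assumed *s* | Recorded | Bias (points) | Athletes missed of 200 | 95% CI half-width (points) |
|---|---|---|---|---|---|
| 10% | 10% | 9% | −1 | 2 | 4.0 |
| 10% | 25% | 7.5% | −2.5 | 5 | 3.7 |
| 10% | 50% | 5% | −5 | 10 | 3.0 |
| 20% | 10% | 18% | −2 | 4 | 5.3 |
| 20% | 25% | 15% | −5 | 10 | 4.9 |
| 20% | 50% | 10% | −10 | 20 | 4.2 |
| 40% | 10% | 36% | −4 | 8 | 6.7 |
| 40% | 25% | 30% | −10 | 20 | 6.4 |
| 40% | 50% | 20% | −20 | 40 | 5.5 |

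Worked case: 0.20 × (1 − 0.25) = 0.15. The absolute bias is 0.20 × 0.25 = 0.05, or 5 points, and 200 × 0.05 = 10 of 40 care-seekers are missed. The bias is then about as large as the sampling half-width of 4.9 points.

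**Step 4: the condition on direction.** If a share *f* of those who did not seek care answered yes, the recorded proportion would be *p*(1 − *s*) + (1 − *p*)*f*. In the worked case *f* would have to reach 0.05 / 0.80 = 6.25% to cancel the shortfall. The downward direction is therefore a tendency that holds when false yes answers are rarer than that.

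**The case against.** Four points can fairly be made for the plan, and each carries some weight.

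- **The questionnaire is not shown.** The protocol summarises a question. The actual wording, examples and response options might make treatment a broad term, and respondents may count advice as treatment. A reader might infer that every athlete who was only assessed or advised is counted as not seeking care. The documents do not support that certainty: they give no coding rule and no narrow definition. What remains is that assessment-only, referral-only and untreated contacts would tend to be missed, and that an undefined word invites different readings.
- **There is a pilot.** It could lead to rewording. But the stated criteria are completion time, relevance and comprehensibility, and an item can satisfy all three while measuring less than its purpose.
- **Aim IV is not left with a single healthcare figure.** It also covers pain medication. The point is limited to the only figure on professionals, and the medication questions do not record contact with one.
- **The variable is descriptive.** It carries no hypothesis or test, so the consequence is confined to one reported percentage.

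A reader might also infer that a low figure would wrongly support the Background's suggestion that MSK pain in E-sport may be unrecognised. The documents do not make that link. The remark follows a comment on scarce data and leads to a call for prevalence studies and for comparisons of training load and physical activity. No section ties it to care-seeking or plans such an inference.

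**Conclusion.** The mismatch is real and small in consequence. The stated purpose and Aim IV are broader than the item as described, nothing else described closes the gap, and the figure on use of professionals would tend to be too low.

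The amount is unknown. In relative terms it equals the share of contacts answered no for want of treatment, and in percentage points it is that share multiplied by the true proportion. Across the assumed ranges (true proportion 10% to 40%, untreated share 10% to 50%) the shortfall runs from 1 to 20 points. None of those inputs comes from the documents, and the calculation takes false yes answers to be absent.

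The primary outcome, MSK pain in the previous week, is unaffected, and so are the comparisons of training load and physical activity in Aims II and III. This is a cheap improvement and does not threaten the study's main conclusions.

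**What to change.** Before the pilot, keep the 3-month window and the reference to MSK pain, and ask whether the athlete has seen or contacted a healthcare professional for MSK pain during the previous 3 months. For those answering yes, add a short follow-up on which profession and whether treatment was given. Report contact as utilization and treatment as a subset of it. The pilot can then check how athletes understand the two terms.

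The cost is one reworded item, one conditional follow-up and a few extra seconds for those who answer yes.

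If the item stays unchanged, label the result as treatment received from a healthcare professional, and do not call it care-seeking or utilization. That needs no new question, but it leaves contacts without treatment unmeasured.

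### The primary prevalence has no clearly prespecified confidence interval, and the plan neither names a site identifier nor allows for recruitment through visited clubs, teams and schools

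*Combined protocol and SAP*

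**What the plan says.** Aim I is the prevalence of musculoskeletal pain, and the primary outcome is any such pain in the previous week, yes or no.

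- **Analysis.** Under Data analysis: "The prevalence of MSK pain within the study population will be presented in absolute numbers and as percentage values". The section's only mention of a CI comes later, in a general sentence that pairs it with means and standard deviations. The sentence after that assigns counts and percentages, with medians and range, to non-parametric data and mentions no CI.
- **Recruitment.** "Members from the research group will subsequently visit clubs, teams and educational institutions who initially shows an interest for the project". At the visit they "distribute the questionnaire to those athletes who wants to participate".
- **Sample size.** The target is 200, and the reason given is: "We estimate that 200 athletes will be an appropriate sample to investigate the prevalence of MSK pain within the E-sport community". No expected prevalence, precision or design effect is stated.
- **Data collected.** Participant characteristics begins: "Enrolled athletes will be asked to provide; name, e-mail, phone number". It goes on to ask "where they participate in E-Sport (e.g. community-based or educational institution". Those examples are types of setting. League and primary game are also asked, but neither is the visited site.

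**The concern.** Aim I is a prevalence, so its uncertainty is a main product of the study. As written, the plan yields either no interval or, if the general CI sentence is stretched to cover a proportion, one that assumes 200 independent athletes.

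Independence is open to doubt because athletes enter in groups. The Perspective section describes teams training with coaches at a physical location, and the protocol hypothesises that pain is related to training load. Team-mates may therefore share exposures. If pain clusters by site, a simple binomial interval is too narrow. Without a recorded site, the study cannot readily show whether this matters.

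**Working it through.** **Inputs.** From the documents: n = 200 (Recruitment), and 41% as an illustrative prevalence (Background: "a small study with 65 participants found that 41% suffered from back or neck pain"). That figure is for back or neck pain, so using it for any musculoskeletal pain is an assumption. Site size m and ICC are not in the documents. I assume m of 5 to 20 and ICC of 0.01 to 0.10.

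**The plan's own figure.** The 200 cannot be reproduced because no inputs are given for it.

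**Independence.** Half-width = 1.96 × √(0.41 × 0.59 / 200) = 6.8 points. It lies between 6.4 and 6.9 for prevalences of 30% to 60%. The Wilson 95% CI for 82/200 is 34.4% to 47.9%.

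**Equal sites.** Design effect DE = 1 + (m − 1) × ICC. Effective n = 200/DE. Coverage of the interval that ignores site = 2Φ(1.96/√DE) − 1. The last column is t(k − 1) × √(0.41 × 0.59 × DE / 200), with k = 200/m sites.

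| m, ICC | DE | Effective n | Coverage ignoring site | Half-width with z | Half-width with t |
|---|---|---|---|---|---|
| 5, 0.01 | 1.04 | 192 | 94.5% | 7.0 | 7.2 |
| 10, 0.05 | 1.45 | 138 | 89.6% | 8.2 | 8.8 |
| 20, 0.10 | 2.90 | 69 | 75.0% | 11.6 | 13.4 |

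For the middle row, t on 19 df is 2.093, and 2.093 × √(0.2419 × 1.45 / 200) = 8.8 points.

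**Simulation.** Beta-binomial data, prevalence 41%, 40,000 replicates. In the three equal-site settings the Wilson interval covers 94.3%, 89.2% and 74.6%. The site-clustered interval (variance factor k/(k − 1), t on k − 1 df) covers 94.8%, 94.8% and 94.7%. In the middle setting its mean half-width is 8.7 points, close to the 8.8 by formula.

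**Unequal sites.** Ten sites of 4, 5, 6, 8, 10, 14, 20, 30, 43 and 60 have a mean size of 20, but what drives the design effect is Σm²/n = 7186/200 = 35.9. At an ICC of 0.05, DE = 1 + 34.9 × 0.05 = 2.75, which implies coverage of about 76% when site is ignored. Simulated coverage:

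| ICC | Wilson, site ignored | Clustered, t on 9 df | Bias-reduced, Satterthwaite df 4.7 |
|---|---|---|---|
| 0 | 94.8% | 92.7% | 95.8% |
| 0.01 | 90.9% | 92.0% | 95.5% |
| 0.05 | 76.0% | 90.2% | 94.3% |
| 0.10 | 63.1% | 89.4% | 93.7% |

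With 20 unequal sites (sizes 3 to 30) the clustered interval covers 94.0%, 93.6% and 93.1% at ICCs of 0.01, 0.05 and 0.10. The bias-reduced version covers 95.0%, 94.6% and 94.2%.

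**Aims II and III.** The variance factor for the group comparison is about 1 + (m − 1) × ICC(variable) × ICC(pain). With m = 10, a pain ICC of 0.05 and a variable ICC of 0.10 to 0.3, it is 1.045 to 1.135. The type I error is then 5.5% to 6.6% by formula and 5.3% to 6.4% for the t-test by simulation.

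**The case against.** - **The harm rests on assumed values.** This stands. At 5 per site and an ICC of 0.01 the effect is negligible. A reader might infer that the interval is bound to be badly wrong, but nothing in the documents shows that pain clusters by site. This is a reason to record site, since the study could then measure the effect.
- **The plan does mention 95% CIs, and anyone can compute one from a count and denominator.** This stands in part. It would go too far to say that the plan excludes an interval for the prevalence. But the CI sentence is tied to means and names no method for a proportion, and an interval computed from the published count assumes independence.
- **Site may be recoverable.** A reader might infer that site information will be lost. The documents do not support that. Names and contact details are collected, the research group visits the sites, and the Method section states: "Participants will be provided with oral and written information regarding the study, before providing written informed consent". The question on where athletes participate might also be free text. Site could probably be traced, but the plan does not provide for it, and tracing afterwards is less reliable than a code.
- **Clustered variance can under-cover.** This stands. With 10 very unequal sites and no clustering it covers 92.7%, below the simple interval's 94.8%. A bias-reduced variance is therefore needed in that layout.
- **Self-selection may matter more.** It may, and a better interval does nothing about it.

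**Conclusion.** The point holds as a gap in the primary analysis that should be closed before enrolment. The text is clear on three things: the prevalence is planned as a count and percentage without a clearly prespecified CI, no analysis allows for site, and no site identifier is named.

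The size of the consequence is not settled by the documents. Under the assumed range it runs from negligible to large. The 75% floor applies only to equal sites; unequal sites reach about the same coverage at half that ICC and fall to 63% at an ICC of 0.10.

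A reader might also infer that the t-tests and rank-sum tests for aims II and III are invalid. They are not shown to be. Inflation requires both pain and the compared variable to cluster by site, and it is small in the middle case, so the planned tests can stay. Confidence is medium, because the ICC and the site layout are unknown.

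**What to change.** 1. Record a site code with each response, for example through one survey link per visited site.
2. Prespecify the primary prevalence as n, % and a 95% CI, with variance clustered on site and t on (sites − 1) df. Use a bias-reduced variance with Satterthwaite df if sites are few or very unequal. Report the simple Wilson interval beside it.
3. If an expected precision is stated, match it to that interval: about ±8.8 points with 20 sites of 10, ICC 0.05 and prevalence 41%, labelled as assumptions. Report the number and size of sites and the observed ICC.
4. State that this does not correct self-selection of sites and volunteers.

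**Cost.** One link per site or one extra field, set up before enrolment, and a few lines of text. If pain does not cluster, the interval is slightly wider: on average 7.0, 7.2 and 7.7 points with 40, 20 and 10 equal sites, against 6.8. The bias-reduced version costs more with 10 very unequal sites (mean 8.7 points at an ICC of 0).
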